3. Alcohol consumptions (AUDIT-C)
4. Stress, measured by means of the Perceived Stress Scale, 4-item
5. Medication Adherence, measured by how many days/weeks the recommended medications are taken, reported by the patient
6. Healthcare access, patients' report on where they normally seek medical care.

After informed consent is obtained, assignment will be unveiled to the participant by the consenting research assistant and the participant will be assigned also with an ID number which will be used in all

procedures using de-identified data.

Participants assigned to the Usual Care (UC) group will be treated using best practice evidence-based discharge procedures, involving a team-based approach to enhance coordination of care for individuals at high risk for readmission.

Participants assigned to the Mi Puente group will be receiving usual care along with the Mi Puente discharge procedure. The latter involves individualized support from a Behavioral Health Nurse while inpatient, a follow-up call from the Behavioral Health Nurse during post-discharge week 1 and weekly supportive phone calls from a Volunteer Peer Mentor during post-discharge weeks 1-4. The intervention will focus on building resources, skills, knowledge and on empowering patients and connecting them with appropriate outpatient services.

EMR of all study subjects will be audited for specific information relevant to the trial (e.g. diagnoses, medication, complications, readmissions, length of stay) at baseline and for readmissions at 30-days and 180-days after baseline.

All study subjects will participate in three assessments of approximately 30-60 minutes duration at baseline and at 3 months and 6 months after baseline. Baseline assessment will be performed prior to hospital discharge in person and the month-3 and month-6 assessments will be conducted by telephone.

Data collected during these assessments will involve the following patient-reported indicators:

1. Demographic information (study-specific/standard item)
2. Physical symptoms, measured via the PHQ-15
3. Quality of life, measured by the PROMIS General Health Scale
4. Healthcare access and barriers, measure adapted from the HCHS/SOL
5. Patient activation, measured by the Patient Activation Measure
6. Support resources for disease management, measured by means of the Chronic Illness Resources Survey.

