Patients interested in the study will be approached by a trained bilingual staff member while inpatient. The bilingual staff member will introduce the study to the participant and obtain verbal consent to administer evidence-based behavioral health screening. Patients who are deemed eligible to participate in the study will be provided with a copy of the consent form and will review all content together with the staff member both in Spanish and English. Adequate opportunity will be provided to the potential participant to consider all options and ask questions; care will be taken to ensure that all participants understand the information and that their participation is voluntary. Prior to each follow-up appointment, research staff will remind participants of the procedures and the voluntary nature of their participation.

Statistical Analysis Plan

Sample size

Power and Sample Size

The target study sample size is 560 participants allocated equally to the two groups ($n = 280/\text{group}$). Sample size estimates were calculated based on the primary outcome of hospital utilization at 30 and 180 days, and the secondary outcome of changes in patient-reported outcomes. All estimates were generated using RMASS2 assuming a statistical significance level of .05 (two-tailed), and targeting at least 80% power. Sample size estimates were adjusted to up to 20% total attrition. Power analyses indicated that a sample size of 558 is needed at baseline to find a statistically significant incidence rate ratio of expected magnitude with 80% power. For patient-reported outcomes, we estimated an effect size of $d = 0.50$ as a clinically significant change. Using parameters defined above, 280 participants are needed to find a statistically significant difference between groups.

Analytic Plan

All analytic strategies will follow intent-to-treat principles. Preliminary data screening and cleaning will be conducted, and statistical testing and effect size consultation will be used to determine if random assignment has resulted in statistical equivalence between groups. Significant covariates will be added to adjust for nonequivalence. Analyses of hospital utilization (primary outcome) and patient-reported

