outcomes will be conducted using multi-level modeling and the appropriate link function for a target outcome. Analyses will include “group” (Mi Puente or Usual) as the between-subjects factor, “time” (assessment dates) as the within-subjects factor, and a cross-level, “group-by-time” interaction effect. Analyses will be conducted in IBM SPSS Statistics 22.0 (IBM, Inc., Armonk, NY, UK) and MPLUS (Muthen & Muthen, Los Angeles, CA, USA). Effect size indicators and confidence intervals will also be examined and reported.

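### The patient-reported analysis makes no use of audited readmission when telephone interviews are missed; using it by arm would remove a small bias that arises if readmission-linked dropout differs between arms

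*Combined protocol and SAP*

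**What the plan says.** Under Analytic Plan, the terms of the multi-level model are given as "Analyses will include “group” (Mi Puente or Usual) as the between-subjects factor, “time” (assessment dates) as the within-subjects factor", together with the group-by-time interaction. One route to further terms is offered: "Significant covariates will be added to adjust for nonequivalence". That sentence concerns imbalance left by randomisation, so it covers baseline variables and would not bring in a readmission that happens after discharge.

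On missing data, the plan says "All analytic strategies will follow intent-to-treat principles" and, under Power and Sample Size, "Sample size estimates were adjusted to up to 20% total attrition". It states no estimator, missingness assumption, auxiliary variable or sensitivity analysis.

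The protocol's description of assessments has month-3 and month-6 patient-reported data collected by telephone. Its description of the EMR audit covers all participants, including "for readmissions at 30-days and 180-days after baseline". After discharge, only Mi Puente has a nurse call in week 1 and "weekly supportive phone calls from a Volunteer Peer Mentor during post-discharge weeks 1-4". Reminders before each follow-up and gift cards (65 dollars in total) apply to both arms.

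**The concern.** A participant who misses both telephone interviews contributes only a baseline score. A likelihood-based model then predicts that person's later scores from participants in the same arm with similar baseline scores who did respond. If the person was readmitted, and readmitted people do worse than their baseline suggests, the prediction is too favourable. The EMR audit records the readmission whether or not the person answers the telephone, but the plan gives that information no role.

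A prediction error of the same size in both arms cancels in the group comparison. An error that differs by arm does not. A difference is possible here, because the arms differ in post-discharge contact and because the intervention aims to change hospital utilisation itself. At stake is the group-by-time effect on the patient-reported outcomes, which are secondary. The primary utilisation outcome comes from the EMR audit and does not depend on interview response.

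**Working it through.** **The plan's own figures.** The plan gives no dropout by arm, readmission rate or score gap, so it has no figure for this bias to reproduce. Its anchors are 560 participants, up to 20% attrition and d = 0.50. The 280 stated for patient-reported outcomes is not used here. A plain two-group comparison at d = 0.50 needs 63 per arm, and 126/0.8 = 158 after attrition; 280 is matched by a change score with within-person correlation 0.11. The correlation and attrition pattern entered in RMASS2 are not given, so this does not show that 280 is wrong.

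**Assumed scenario (none of it from the documents).** Readmitted: 30% in both arms. Interviews missed by readmitted participants: 50% in Usual Care, 25% in Mi Puente. Missed by others: 15% and 12%. Readmitted people score δ = 0.5 to 0.8 SD worse at follow-up, with higher scores taken as better.

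**Step 1: who responds.**
- Usual Care: responding 0.3×0.50 + 0.7×0.85 = 0.745, of whom 0.150/0.745 = 20.1% were readmitted.
- Mi Puente: responding 0.3×0.75 + 0.7×0.88 = 0.841, of whom 0.225/0.841 = 26.8% were readmitted.
- Attrition is 25.5% and 15.9%, averaging 20.7%, close to the planned ceiling.
- Difference in respondent mix: 0.2675 − 0.2013 = 0.0662.

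**Step 2: bias with no true effect.** Let k be the share of the gap δ already visible at baseline and β the slope of the month-6 score on baseline. If every non-responder misses both interviews, the likelihood model overstates an arm's mean by δ × (0.30 − share readmitted among respondents) × (1 − βk). The bias of the group contrast is then −δ × 0.0662 × (1 − βk). With β of about 0.5:

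| Share of gap at baseline | δ = 0.5 | δ = 0.8 |
|---|---|---|
| none (k = 0) | −0.033 | −0.053 |
| half (k = 0.5) | −0.025 | −0.040 |
| all (k = 1) | −0.017 | −0.026 |

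The first row is also the plain comparison of respondents; the model does no better only when baseline carries no information about later readmission. If half of the non-responders answer at month 3, the bias shrinks further. Maximum-likelihood simulation of this scenario with within-person correlation 0.5 gave −0.013 to −0.054 SD. With correlation up to 0.7 and half answering at month 3, the low end is −0.008.

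**Step 3: other dropout patterns.**
- Same pattern in both arms, equal readmission: bias 0. With readmission 40% v 30%: −0.002 to −0.008 SD.
- Mild difference (readmitted lost 35% v 30%, others 15% v 14%): shares 0.195/0.790 = 0.247 and 0.210/0.812 = 0.259. With δ = 0.8 and k = 0.5, bias = −0.8 × 0.0118 × 0.75 = −0.007 SD.
- Stronger differences (readmitted lost 35-45% v 5-20%; readmission 40% in Usual Care and 30% or 40% in Mi Puente; δ 0.3-0.8): about −0.02 to −0.08 SD.
- Dropout rates swapped between arms: same size, opposite sign.

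**Step 4: with the auxiliary variable.** Adding readmission by arm brought the simulated estimate to within 0.003 SD of the truth in the main scenario and within 0.004 SD in the wider set.

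**Step 5: scale.** With 560 × 0.8 = 448 analysed, the standard error is 2/√448 = 0.094 SD. This also holds for a change score at correlation 0.5, since √(2(1 − 0.5)) = 1. A bias of 0.013 to 0.053 is 0.14 to 0.56 standard errors, and 3% to 11% of d = 0.50. Power at d = 0.50 stays above 99%. The effect detectable with 80% power is about 0.26. There, power falls to Φ(0.84 − 0.14) = 76% at the low end and Φ(0.84 − 0.56) = 61% at the high end. At the high end, two-sided type I error rises from 5% to about 9%.

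**The case against.** The strongest reply is that the bias needs an arm difference in readmission-linked dropout that the documents do not show. They give one attrition figure, not split by arm. They describe the nurse and peer calls as intervention, and those calls end in week 4, well before the month-3 interview. The stated retention measures are the same for both arms. All of this stands. A reader might infer that the Mi Puente calls keep people in the study and that loss will therefore differ; the documents do not support that beyond a possibility.

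A reader might also infer that the model treats dropout as unrelated to readmission, or that it can correct none of the resulting bias. Neither follows. A likelihood fit allows dropout to depend on arm, visit, added covariates and observed scores, so it removes part of the bias whenever those scores carry information about readmission. Nor is the model confined to three terms, given the provision for imbalance covariates.

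Finally, the effect is small, confined to secondary outcomes, and in the main scenario conservative for Mi Puente. That is true of that scenario only, since the opposite pattern would favour Mi Puente. The plan neither states that the pattern is the same in both arms nor provides for checking it.

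**Conclusion.** The point holds as a low-cost improvement to the secondary analyses. The text establishes three facts: no missing-data method is stated; readmission is recorded for all participants; and nothing in the patient-reported model uses it. That readmission predicts missed interviews and worse scores is plausible but assumed.

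The bias is roughly 0.01-0.05 SD under the main assumed scenario, up to about 0.08 SD under stronger arm differences, and about zero if the dropout pattern is the same in both arms. It would not threaten detection of d = 0.50, but it matters for effects near 0.26. The documents do not support a claim that the result will be biased, or biased against Mi Puente: both the existence and the sign of the bias depend on a dropout pattern not yet known.

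**What to change.** Keep the stated model and add to the Analytic Plan:

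1. **Assumption and estimator.** State that patient-reported outcomes are analysed by full-information maximum likelihood in Mplus, which the plan already names, and state the missing-data assumption.
2. **Auxiliary variables.** Include EMR readmission by 30 days and by 180 days as auxiliary variables, with their relations to the scores allowed to differ by arm. Multiple imputation carried out separately in each arm is an equivalent route. Do not enter readmission as a covariate: it follows randomisation and may carry part of the treatment effect.
3. **Reporting.** Tabulate month-3 and month-6 interview completion by arm and readmission status, so that the size of any arm difference can be seen.
4. **Sensitivity.** Add one analysis that shifts the imputed scores of non-responders in the unfavourable direction, in each arm, by a prespecified range.

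The cost is SAP wording, some analysis time and a slightly more complex model; no new data, contacts or participants are needed. The benefit depends on how completely the audit captures readmissions. The documents do not say whether admissions to other hospitals are included, and the plan should state this.

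### For continuous patient-reported outcomes, the planned group-by-time model leaves baseline free to differ by arm and so gives wider intervals than the collected data allow

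*Combined protocol and SAP*

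**What the plan says.** The Mi Puente Protocol has every participant assessed "at baseline and at 3 months and 6 months after baseline". The first assessment is in person before discharge and the later two are by telephone.

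The Analytic Plan uses multi-level models, with a link function suited to each outcome, for both hospital utilization and patient-reported outcomes. Group is the between-subjects factor. Time is described by the words "assessment dates) as the within-subjects factor". A group-by-time interaction completes the model. The equation, the coding of time and the contrast to be reported are not written out.

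Nothing sets the baseline means equal or names the baseline value as a covariate in advance. The only adjustment depends on the data: "Significant covariates will be added to adjust for nonequivalence".

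Under Power and Sample Size, changes in patient-reported outcomes are the secondary outcome. For these, "we estimated an effect size of $d = 0.50$ as a clinically significant change".

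**The concern.** Baseline is one of the assessment dates and group is a main effect. On the natural reading, the model therefore estimates a baseline difference between arms, and the interaction measures how far the later difference departs from it. If baseline is measured before allocation can influence it, the true baseline difference is zero by randomization. Estimating that difference and subtracting it adds sampling noise to the treatment contrast.

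The plan commits to reporting effect sizes and confidence intervals, so this noise would show directly as wider intervals for the continuous patient-reported scores.

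Changing the covariate rule alone would not settle the matter. Baseline cannot sensibly be both a repeated outcome and a covariate in the same model, so the sentence that defines the model needs its own edit.

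**Working it through.** **Inputs from the SAP (Power and Sample Size).**
- Error rate and power: "assuming a statistical significance level of .05 (two-tailed), and targeting at least 80% power".
- Size: "The target study sample size is 560 participants allocated equally to the two groups", that is 280 per arm.
- Attrition: "Sample size estimates were adjusted to up to 20% total attrition".
- Planned effect: d = 0.50. The SD that standardizes it is not stated.

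**Assumptions (not in the documents).** Baseline-to-follow-up correlation rho from 0.3 to 0.8; equal variances and equal correlations across the three visits; attrition split as 10% lost before month 3 and a further 10% before month 6; a continuous outcome with identity link.

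**Step 1: the plan's own figure.** The SAP says that 280 participants are needed for patient-reported outcomes. The two-means formula gives 2 × (1.960 + 0.842)² / 0.50² = 62.8, so 63 per arm and 126 in total. With 20% attrition, 126 / 0.80 = 157.5, so 158. The printed inputs therefore do not reproduce 280. A change-score variance of 2(1 − rho) with rho = 0.11 does: 62.8 × 1.78 = 111.8, so 112 per arm, 224 in total, and 224 / 0.80 = 280. The SAP states no rho, contrast or number of time points for its sample-size program. This is a gap in documentation and does not show that 280 is wrong. Nothing below depends on it.

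**Step 2: month-6 contrast, complete data.** In units of the raw-score variance, with n per arm:
- free baseline (difference in change): (2/n) × 2(1 − rho)
- common baseline: (2/n) × (1 − rho²)
- ratio: (1 − rho²) / [2(1 − rho)] = (1 + rho)/2

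The ratio is 0.65, 0.75 and 0.85 at rho = 0.3, 0.5 and 0.7. It is below 1 for every rho below 1, so the direction does not depend on the assumed value.

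**Step 3: the three-visit design with 20% attrition.** Generalized least squares variances with 280 per arm at baseline and d on the raw-score SD. Each pair of figures is free baseline, then common baseline.

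| rho | Variance ratio | Interval width ratio (square root) | Detectable d at 80% power | Power at an illustrative d = 0.25 |
|---|---|---|---|---|
| 0.3 | 0.698 | 0.835 | 0.301, 0.252 | 64%, 79% |
| 0.5 | 0.787 | 0.887 | 0.257, 0.228 | 78%, 87% |
| 0.7 | 0.874 | 0.935 | 0.200, 0.187 | 94%, 96% |
| 0.8 | 0.917 | 0.958 | 0.164, 0.157 | 99%, 99% |

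Intervals narrow by about 16%, 11%, 7% and 4%. The gain is smaller than with complete data. Participants lost to follow-up still contribute a baseline value, which helps the free-baseline model to estimate the baseline difference it subtracts.

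**Step 4: power at the planned effect.** At d = 0.50 the lowest power in these settings is 99.6% (free baseline, rho = 0.3, 20% attrition). If d is instead standardized by the SD of change, 280 × 0.80 = 224 completers per arm give above 99.9% with the plain change contrast.

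**The case against.** The strongest reply is that this is a choice of efficiency and not an error. Group-by-time is an unbiased test under randomization and matches the SAP's stated interest in change. These outcomes are secondary, and the trial's size is set by hospital utilization, for which 558 are said to be needed. Even the less precise model has ample power at d = 0.50. All of this stands. A reader might infer that the planned test is biased or that the patient-reported outcomes are underpowered; the documents and Step 4 support neither.

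Other limits also stand:
- **Size.** A reader might take the complete-data ratios (0.65, 0.75, 0.85) as the gain. The plan allows for up to 20% attrition, so the Step 3 figures are the fair ones.
- **Scope.** The formula does not carry over directly to outcomes with a non-identity link. The SAP leaves the link open, and the protocol does not give the scale of the adapted healthcare access and barriers measure. The point does not extend to hospital utilization.
- **Order of baseline and assignment.** The protocol unveils assignment after consent and places baseline before discharge, but does not say which comes first. Mi Puente nurse support also starts during the stay. Equal baseline means therefore cannot be taken for granted.
- **Choice of visit.** A reader might infer that month 6 should be the single reported effect. Nothing in the documents ranks it above month 3, and the precision argument does not choose between them.
- **Equivalence.** The common-baseline and baseline-covariate models can use different participants when values are missing, so they are alternatives and not strictly the same analysis.

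The reply does not remove the gain itself: the baseline scores are already collected, and effects smaller than 0.50 are possible.

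**Conclusion.** The point holds as a low-cost gain in precision for continuous patient-reported outcomes. As written, the model is valid but gives wider intervals than necessary. With 20% attrition, the common-baseline variance at month 6 is about 0.70, 0.79 and 0.87 of the free-baseline variance at rho = 0.3, 0.5 and 0.7. The benefit is tighter intervals and more power for effects below the planned one.

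The direction holds for any rho below 1, given a baseline unaffected by assignment. The size rests on the assumed correlations, correlation structure and attrition pattern. The free-baseline reading is inferred from the listed factors, because no equation is given. The significance-triggered covariate rule is a separate matter and adds no weight here.

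**What to change.** In the Analytic Plan, for continuous patient-reported outcomes only, replace the group, time and group-by-time specification with one of these, chosen before analysis:

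1. a repeated-measures model with a common baseline mean: no group effect at baseline, terms for time, and group-by-follow-up-visit terms for months 3 and 6; or
2. a model for months 3 and 6 with the outcome's own baseline value as a covariate.

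Report the group difference with its confidence interval at each follow-up visit. State which participants each analysis uses when baseline or follow-up values are missing.

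Confirm from study records that baseline was completed before assignment was unveiled, and apply the common-baseline constraint only where that order holds. Baselines taken after unveiling could also distort the current change contrast, so the check is useful under either model.

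**Cost.** The analysis change is SAP wording; it needs no new data, and the mixed models in the named software can fit it. If baseline does not already precede unveiling, making it do so is a change in field procedure and not only in text. It could not be applied to those already enrolled: on the protocol's timeline enrollment opened in month 7 (January 2016), about a year before the document date of January 24, 2017.
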